7.2.3 Clinical status

Clinical status will be assessed through determination of the following:

- Infections will be determined and defined as either:
 - Clinically documented subjects with documented signs and symptoms of infection without positive microbiologic cultures
 - Microbiologically documented subjects with documented signs and symptoms of infection and with positive viral or bacterial cultures
- Hospitalizations incidence and duration of hospitalizations through completion of the study
- Growth height, weight and growth curve determinations through completion of the study (Note: this assessment should be done for subjects < 18 years of age)
- Overall survival through the end of the study

Infections will be extracted from the adverse event dataset as all reported adverse events where the question "Is this event an Infection?" is answered by "Yes" and the Classification is reported as "Clinically documented" or "Microbiologically documented". Events classified as "Unknown" will not be included in the analysis of the infections. However, events classified as Unknown will be included in the analysis of the adverse events as part of the safety analysis (see section 8.2). The following time periods will be analyzed:

1. The year prior to treatment start with Revcovi (study day -365 to -1)

- 2. From Treatment initiation until 1 year after treatment initiation with Revcovi (Study day 1 to 365)
- 3. From one to 2 years after treatment initiation with Revcovi (Study day 366 to 730).
- 4. From 2 to 3 years after treatment initiation with REVCOVI (Study days 731 to 1095)
- 5. From 3 to 4 years after treatment initiation with REVCOVI (Study days 1096 to 1461).
- 6. From 4 to 5 years after treatment initiation with REVCOVI (Study days 1462 to 1826).
- 7. From 5 to 6 years after treatment initiation with REVCOVI (Study days 1827 to 2191).
- 8. From 6 to 7 years after treatment initiation with REVCOVI (Study days 2192 to 2556).
- 9. From 7 to 8 years after treatment initiation with REVCOVI (Study days 2557 to 2921).
- 10. From 8 to 9 years after treatment initiation with REVCOVI (Study days 2922 to 3286).
- 11. At any time after treatment initiation with REVCOVI (Study day 1 onwards)

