For the STP-2270-002 subjects, the observational period for infections and hospitalizations after treatment initiation starts at the first dose of REVCOVI in the CLI-06814AA1-01 study. Infections and hospitalizations occurring during the STP-2279-002 study will not be included in the summary tables for the CLI-06814AA1-01 study.

The time periods will be defined as follows:

The year prior to treatment start with Revcovi will be defined as study day -365 to study day -1. For subjects younger than 1 year of age at the time of treatment initiation with Revcovi, it will be defined as the time period from the date of birth until study day -1 (time period calculated as date of first dose of Revcovi - date of birth + 1 day).

The end date of the time periods 1, 2, 3, 4, 5, 6, 7, 8, and 9 years after treatment initiation of Revcovi, respectively, will be defined as the earliest of the following events:

- End of time period (study day 365, 730, 1095, 1461, 1826, 2191, 2556, 2921, and 3286 respectively)
- Last date of treatment with Revcovi + 30 days
- Study completion date
- Study discontinuation date

- Date of death
- Date of transplantation

Infections occurring more than 30 days after the last dose of Revcovi will not be included in the calculation of the incidence rates, but will be included in the data listings and flagged.

The following analyses will be performed for the infections for each time period defined above:

- Number of events, number and percentages of affected subjects by SOC and PT. The denominator for the calculation of the percentages is the number of subjects with an observational period of 1 day or more in the respective analysis period, i.e. if the end date as defined above is not prior to the start date of the respective analysis period.
- Incidence rate of infections (in number of infections per year). The incidence rate will be based on the number of events, not on the number of affected subjects.
 95% CIs will be calculated for the incidence rates by the method of Ulm, assuming a Poisson distribution. The total observational period will be defined as the sum of the time periods for each subject from the start until the end date of the respective time period as defined above (end date start date + 1 day).

For both analyses, the infections will be slotted to the analysis periods based on the onset date of the adverse event.

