14. PROGRAMMING SPECIFICATIONS

- The following algorithm should be used to estimate adverse event start dates for which only partial information is known. To conservatively assign start dates as early as possible, the first day on study drug is the reported start date of Revcovi in the CLI-06814AA1-01 study.
 - Missing day and month
 - If the year is the same as the year of first day on drug, then the day and month of the start date of drug will be assigned to the missing fields.
 - If the year is prior to the year of first day on drug, then December 31 will be assigned to the missing fields.
 - If the year is after the year of first day on drug, then January 01 will be assigned to the missing fields.
 - Missing month only
 - Treat day as missing and replace both month and day according to the above procedure.
 - o Missing day only
 - If the month and year are the same as the year and month of first day on drug, then the start date of drug will be assigned to the missing day.
 - If the month and year are before the year and month of first day on drug, then the last day of the month will be assigned to the missing day.
 - If the month and year are after the year and month of first day on drug, then the first day of the month will be assigned to the missing day.

If the resultant imputed start date is after the AE stop date (and the AE stop date is complete), the imputed start date will be reset to the AE stop date.

- Adverse events with partially missing stop dates and the outcome is "Resolved" or "Resolved with sequelae" will have stop dates imputed as follows:
 - *year is missing* date left missing.
 - o month is missing impute 'December'.
 - o *day is missing* impute 'last date of that month'.

- It is assumed that for the start and stop date of Revcovi, at least month and year are known. If day is missing, it will be imputed by the first of the month, if necessary.
- Partially missing start dates for Adagen pre-treatment (Adagen transitioning patients) will be imputed as follows:
 - Day is missing impute 01 of the month
 - Day and month is missing: impute 01July.
- It is assumed that at least month and year is known for the QoL questionnaires, physical examinations, vital signs, and other laboratory data. If the day is missing, day will be imputed by the 15th of the month. If month and/or year is missing, the records will be excluded from all analyses.
- Partially missing dates for the diagnosis of ADA-SCID will be imputed as follows:

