 - Year is missing impute with date of birth
 - Month is missing and year is available impute by 01 January. If the imputed date is prior to the date of birth, impute date of birth.
 - Day is missing impute first day of month. If this imputed date is prior to the date of birth, impute date of birth.
- Complete dates for concomitant medications with missing or partially missing start dates will be imputed, if necessary, using the same algorithm described for adverse event onset dates. If the stop date is missing or partially missing and the "ongoing" variable is indicated as 'no', the imputation rule is applied in the following order:
 - *year is missing* the medication will be considered to have been received at all periods after that period determined by the start date. Date is left missing.
 - o month is missing impute 'December'.
 - o *day is missing* impute 'last date of that month'.
- The following algorithm should be used, when necessary, to calculate a start date that is partially missing for medical history:
 - missing day and month January 01 will be assigned to the missing fields.
 - *missing month only* treat day as missing and replace both month and day according to the above procedure.
 - *missing day only* assign first of the month to the missing day.
- Partially missing stop dates will be imputed as:
 - *year is missing*, no imputation. Date left missing.

- *month is missing and year is prior to year of first dose of study medication*impute 'December'.
- month is missing and year the same as the year of the first dose of study medication impute same month as in start date.
- \circ day is missing: impute 'last date of that month'. If this results in a date \geq the date of the first dose of study medication, impute day as the day prior to the first dose of study medication.
- Partial missing death dates will be imputed in the same way as adverse event start dates.
- Date imputations will be applied to the process of assigning study day and should be retained in the analysis datasets, but the data listings should display the original, partially missing dates.
- Adverse event summary tables will only include treatment-emergent AEs. However, listings will include all AEs (i.e., treatment-emergent and non treatment-emergent AEs) with the non treatment-emergent AEs flagged.

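### The rule for completing partial adverse event onset dates also decides the infection period, so infections dated only to a calendar year inflate Revcovi year 1

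*SAP*

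**What the plan says.** SAP Section 7.2.3 builds the infection analysis on adverse event data: "Infections will be extracted from the adverse event dataset as all reported adverse events where the question" on infection is answered yes and the infection is classified as clinically or microbiologically documented. This covers the pre-treatment year (study day -365 to -1), year 1 (study day 1 to 365) and the later yearly periods. The same section adds: "For both analyses, the infections will be slotted to the analysis periods based on the onset date of the adverse event". Each period's rate is events divided by summed observation time, with a Poisson confidence interval. SAP Section 8.2 counts infections among the efficacy measures.

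SAP Section 13.5 sorts adverse events into pre-treatment, treatment-emergent and post-treatment, and sends partially missing onset dates to Section 14. For an onset known only to the year, Section 14 has three clauses:

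- Same calendar year as the start: "If the year is the same as the year of first day on drug, then the day and month of the start date of drug" fill the missing fields.
- Earlier year: "If the year is prior to the year of first day on drug, then December 31 will be assigned to the missing fields".
- Later year: 1 January is used.

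If only the day is missing, the analogous dates are the start date, the last day of the month and the first day of the month. A closing step resets an imputed start to the stop date when the stop date is complete and earlier. Section 14 then says: "Date imputations will be applied to the process of assigning study day". It makes no exception for infections. The remark in Section 13.3 that missing data are not imputed does not displace this, because Sections 13.5 and 14 expressly impute onset dates.

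**The concern.** For treatment-emergent status the rule is cautious, since an ambiguous event near the start of treatment is counted as on-treatment. A rate by period has no cautious side. Moving an event takes it from one numerator to another while both denominators stay as they were.

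At stake are the infection rates before and after Revcovi. Protocol Section 13.2.3 has each subject serve as his or her own control where appropriate, so readers will compare the pre-year with year 1. The planned confidence intervals do not reflect dating error. Protocol Sections 7.1 and 11.1 allow retrospective collection of pre-treatment history and of data on subjects already on Revcovi, where partial dates are plausible. For infants the pre-treatment period runs only from birth, so a few events can change its rate.

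**Working it through.** The plan gives no infection rate, sample size or share of partial dates, so it has no figure to reproduce.

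**Step 1: one start date.** Take a start on 1 July 2019 and apply the Section 14 clauses to onsets known only to the year, with no complete stop date.

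| Onset year | Imputed date | Study day | Period assigned | Where the possible days lie |
|---|---|---|---|---|
| 2018 | 31 Dec 2018 | -182 | pre-year | 181 before the look-back, 184 in the pre-year |
| 2019 | 1 Jul 2019 | 1 | year 1 | 181 in the pre-year, 184 in year 1 |
| 2020 | 1 Jan 2020 | 185 | year 1 | 181 in year 1, 185 in year 2 |

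Year 1 receives the year-only onsets of two calendar years.

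**Step 2: average over start dates.** Assumptions not in the documents: constant true infection rate, start dates uniform over the calendar year, and a share f of infections with year-only onset. Set the true year-only count in each full year to 1.

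*History limited to 12 months, no complete stop date.* On average half of the pre-year falls in the start's calendar year and moves to Day 1. Half of year 2 falls in the next calendar year and moves to 1 January, which lies in year 1 (except for a start on or right after 1 January).

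- Pre-year: 1 - 0.5 = 0.5
- Year 1: 1 + 0.5 + 0.5 = 2.0
- Rate ratio, year 1 to pre-year: (1 - f + 2f)/(1 - f + 0.5f) = (1 + f)/(1 - f/2)

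*History limited to 12 months, complete stop date.* Assume a 14-day infection. The reset returns a pre-year onset to its own stop date unless that date reaches the start of treatment, so only about 14/365 = 0.04 of the pre-year still moves. The year-2 shift is untouched, because 1 January precedes the stop date.

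- Pre-year: 1 - 0.04 = 0.96
- Year 1: 1 + 0.04 + 0.50 = 1.54
- Rate ratio: (1 + 0.54f)/(1 - 0.04f)

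| f | No complete stop date | Complete stop date |
|---|---|---|
| 5% | 1.05/0.975 = 1.08 | 1.027/0.998 = 1.03 |
| 10% | 1.10/0.95 = 1.16 | 1.054/0.996 = 1.06 |
| 20% | 1.20/0.90 = 1.33 | 1.108/0.992 = 1.12 |

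The correct value is 1.00 throughout. A simulation of 200,000 events per scenario gave pre-year and year-1 factors of 0.50 and 1.99 without complete stop dates, and 0.96 and 1.54 with them.

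**Step 3: the 31 December clause.** It misplaces events only if infections older than 12 months were also entered. Without complete stop dates, the older events pulled in then roughly replace those lost to year 1: the simulated factors are 0.99 for the pre-year and 2.01 for year 1.

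**Step 4: only the day missing.** Without complete stop dates, the simulated factors are 0.96 and 1.08. If 10% of onsets lacked only the day, the ratio would be (1 + 0.08 × 0.10)/(1 - 0.04 × 0.10) = 1.008/0.996 = 1.01.

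**Step 5: STP-2279-002 subjects.** Section 14 anchors the imputation at the CLI-06814AA1-01 start date. Suppose an infection occurred during STP-2279-002 in that same calendar year, is dated only to the year and has no complete earlier stop date. It is moved to the registry start. Section 7.2.3 opens the infection period for these subjects there and excludes STP-2279-002 infections from the summaries, so the event enters tables that should omit it.

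**The case against.** The strongest reply is the stop-date reset. A reader of the three clauses might infer that every year-only onset in the start year is counted in year 1, and that every prior-year onset falls inside the look-back. The documents do not support that. With a start on 1 October 2019, an onset in 2019 with a stop on 20 March 2019 is reset to day -195, in the pre-year. An onset in 2018 with a stop on 10 March 2018 is reset to day -570, outside the look-back. This stands: complete stop dates largely protect the pre-year. They do not stop the shift from year 2 into year 1.

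Protocol Sections 10.3 and 11.1 ask for infection history over the past year only. If sites kept to that, a prior-year infection belongs in the look-back and 31 December puts it in the right period. This also stands.

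The extent of partial dating is unknown. Protocol Sections 10.5.5 and 12.3 require an onset date, and Section 14.7.1 describes data queries. Hence the size can only be shown as a range.

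Finally, the analysis is descriptive, with no test and no planned before/after ratio. That limits the consequence, but a per-period efficacy rate can still be wrong without a test.

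**Conclusion.** The concern holds. SAP Sections 7.2.3 and 14 together let a rule made for treatment-emergent status assign infections to yearly efficacy periods. Year 1 is inflated, through the start-year and later-year clauses. The pre-year is deflated mainly when stop dates are incomplete.

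For year-only shares of 5% to 20%, the year-1 to pre-year ratio is 1.08 to 1.33 without complete stop dates and about 1.03 to 1.12 with them, against a true 1.00. These figures rest on a constant true rate, uniform start dates, a 12-month history and, in the second case, a 14-day infection. The effect is small if only the day is missing and zero if no onset is partial.

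A reader might infer that the rule flatters Revcovi. The calculations do not support that: in every scenario year 1 rises relative to the pre-year, which works against the drug. Nor should much rest on the Section 14 sentence about assigning early dates. It introduces the choice of anchor date, and its tension with the 31 December clause is secondary.

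**What to change.** Restrict the Section 14 onset algorithm to treatment-emergent classification. For the infection periods, derive a second onset date from the feasible interval, bounded by birth, a complete stop date and the known date parts. Use either the interval midpoint or allocation in proportion to the feasible days in each period. The midpoint is simpler but is still one fixed date: for a 1 October start it falls about 2 July, so every unbounded start-year onset would go to the pre-year although about 25% of that year (92/365) is on drug. Proportional allocation avoids this.

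Report the number of imputed onsets per period. Where there are any, show the rates with all partial dates placed in the earliest and then in the latest feasible period. Check STP-2279-002 subjects separately, so that an infection from that study is not moved into the registry summaries.

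The cost is SAP wording, one more derived variable and one sensitivity table. The count of imputed onsets alone would show whether the problem is material.

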8.2 Adverse Events and Other Complications

As part of this registry, only infections, clinically meaningful laboratory abnormalities (except infections) and Revcovi related adverse events will be recorded in the eCRF. A treatment-emergent AE will be defined as an AE with an onset date at or after the reported start date of Revcovi in the CLI-06814AA1-01 study and no later than 30 days after the last dose of Revcovi. All adverse events will be coded using the Medical Dictionary for Regulatory Activities (MedDRA) Version 22.1 or the most recent version prior to database lock. Summaries will be presented for all treatment-emergent adverse events (overall and by severity), adverse events determined by the investigator to be treatment-related (overall and by severity), serious adverse events (SAEs), adverse events causing discontinuation from Revcovi, and non-serious AEs. In addition to being summarized as adverse events, infectious complications and hospitalizations are considered efficacy measures as summarized in Section 7.2.3.

The frequency of adverse events will be summarized using descriptive statistics by system organ class (SOC), preferred term and subject status. Subjects are counted only once in each SOC category, and only once in each preferred term category. Treatment-related adverse event summaries will include adverse events with missing relationship to study drug. For the summaries by severity, subjects with multiple events are counted only once at the greatest non-missing severity. If all are of missing severity grade, then the AE term (SOC or PT) will be included in "Missing" severity category. Adverse events missing the flag indicating serious will be excluded from the summary of serious adverse events but included in the summary of non-serious adverse events. The total number of adverse events and serious adverse events and the corresponding yearly rates will also be reported.

Listings for all adverse events, deaths, serious adverse events and adverse events leading to study drug discontinuation will be presented. AEs from STP-2279-002 subjects with an onset date prior to the first documented dose of Revcovi in the CLI-06814AA1-01 study and a resolution date after the reported start date of Revcovi in the CLI-06814AA1-01 study or an outcome of ongoing, will be included in the AE listings but not in the summary tables.

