13.2 Assignment of Study Days

For the purposes of data listings and summaries, "Study Day" will be calculated relative to the reported first dose of Revcovi, which is for the STP2270-002 patients, the reported date of the first dose of Revcovi in the STP-2279-002 study (i.e., date of interest – reported date of first dose of Revcovi). One day will be added if this difference is ≥ 0 , so that the first dose of study medication is considered "Study Day 1." The day prior to the first dose of study medication is considered "Study Day -1". For analysis purposes, there will be no "Study Day 0".

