13.5 Safety Data Handling

For the purposes of AE reporting, three time periods will be defined based upon the onset date of the AE:

- "Pre-treatment AEs" are AEs with onset dates < date of the reported start date of Revcovi in the CLI-06814AA1-01 study.
- "Treatment-emergent AEs" are AEs with onset dates ≥ date of the reported start date of Revcovi in the CLI-06814AA1-01 study and within 30 days following the date of the last dose of Revcovi.
- "Post-treatment AEs" are AEs with onset dates > 30 days after the date of the last dose of Revcovi within study CLI-06814AA1-01.

"Pre-treatment" and "Post-treatment" AEs are considered non-treatment-emergent AEs. For AEs with partially missing onset dates, an onset date is imputed as detailed in Section 14 (Programming Specifications). If an AE has a completely missing onset date, it is counted as a "treatment-emergent" event, unless the stop date is on or before the date of the first dose of study medication.

If relationship to study drug is missing, for analysis purposes it will be assumed to be related to study drug. For AEs which occur more than once within a time period (see above), the AE which is most related to study drug in that time period will be used in the summary of AEs by categories of relationship to study drug. Similarly, the AE with the maximum intensity in that time period will be used in the summary of AEs by categories of severity.

Concomitant medication of interest is any anti-infective medication applied on or after the reported start date of Revcovi in the CLI-06814AA1-01 study, including medication which was initiated prior to the reported start date of Revcovi in the CLI-06814AA1-01 study and continued until or after the reported start date of Revcovi in the CLI-06814AA1-01 study. Imputation rules for partially missing start/stop dates are described in Section 14 (Programming Specifications).

Change from baseline to Week X in safety endpoints will be calculated in the same way as for the efficacy end points.

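### SAP 14 does not check a year-only adverse event onset against a month-and-year stop date, so an event that ended before Revcovi can be tabulated as treatment-emergent

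*SAP*

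**What the plan says.** SAP 14 imputes partial adverse event (AE) onset dates, taking the registry's reported Revcovi start as the first day on drug.

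- Day and month missing, year equal to the year of Revcovi start: "then the day and month of the start date of drug will be assigned to the missing fields".
- Only the month missing: "Treat day as missing and replace both month and day according to the above procedure".
- Only the day missing, month earlier than the Revcovi month: "then the last day of the month will be assigned to the missing day".

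One consistency check follows. It begins "If the resultant imputed start date is after the AE stop date (and the AE stop date is complete", where the bracket closes, and it resets the imputed onset to the stop date. The next bullet imputes partial stop dates of resolved events: a missing day becomes the last day of the month, and a missing month becomes December. No rule compares the imputed onset with the imputed stop.

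SAP 13.5 deals separately with a completely missing onset. Such an event is treatment-emergent "unless the stop date is on or before the date of the first dose of study medication". That exclusion does not require a complete stop date.

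SAP 14 also limits the AE summary tables to treatment-emergent events and uses imputed dates to assign study days. SAP 7.2.3 takes infections from the AE dataset and places them in analysis periods by onset date. One of those periods is the year before Revcovi.

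**The concern.** The imputed onset decides whether an event is tabulated. Treating an event as treatment-emergent when its timing is uncertain is a sound convention. Here the timing is not uncertain in the way that matters: if the stop month lies wholly before Revcovi start, the missing day cannot change the classification. The stated aim of the algorithm is to date onsets early, yet in this case it dates the onset after the event has ended.

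Two sets of results are exposed. The first is the treatment-emergent AE tables and the yearly AE rates of SAP 8.2. The second is the infection comparison of SAP 7.2.3. Protocol 13.2.3 makes each subject his or her own control. An affected infection lowers the pre-Revcovi count by one and raises the year 1 count by one, so the difference shifts by two events against Revcovi.

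Partial dates are plausible. Protocol 7.1 and 11.1 call for retrospective collection and for infections over the preceding 12 months.

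**Working it through.** The plan states no figure to reproduce. The check applies the rules literally.

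**Worked case (dates assumed).** Revcovi start 15 June 2020, outcome resolved.

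| Onset recorded | Stop recorded | Imputed onset | Stop after imputation | Reset? | Class |
|---|---|---|---|---|---|
| 2020 | Mar 2020 | 15 Jun 2020 | 31 Mar 2020 | No, stop not complete | Treatment-emergent |
| 2020 | 31 Mar 2020 | 15 Jun 2020 | 31 Mar 2020 | Yes, to 31 Mar | Pre-treatment |
| Missing | Mar 2020 | none | 31 Mar 2020 | SAP 13.5 applies | Not treatment-emergent |

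Row 1: the gap from 31 March to 15 June is 30 + 31 + 15 = 76 days. Rows 1 and 2 end on the same date after imputation but are classed differently. Row 3 takes SAP 13.5 to use the imputed stop. On that reading, knowing the onset year gives a worse classification than knowing nothing about the onset.

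**Infection period.** With the reset, the onset in row 1 would be 31 March, which is Study Day −76 and lies in the pre-Revcovi window (days −365 to −1). Without it, the onset is Study Day 1, in year 1. This holds for Adagen-naïve and Adagen-transitioning subjects. For STP-2279-002 subjects, SAP 13.2 counts study days from the earlier study's first dose, so the shift does not take this form.

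**Which patterns fail.** I crossed four states of onset (complete, month-year, year only, missing) with three of stop (complete, month-year, year only), giving 12 patterns. The assumed grid had Revcovi start on each day of 2020, onsets 1 to 730 days earlier in steps of three days, and durations of 0, 7, 14, 30 and 90 days. I counted cases whose latest possible stop precedes Revcovi and that the rules still class as treatment-emergent.

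- Year-only onset with month-year stop: 87,464 of 419,711 (87,464 / 419,711 = 20.8%).
- Each of the other 11 patterns: 0.

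The failure needs all three of these: onset month unknown, onset in the calendar year of Revcovi start, and a month-year stop in an earlier month of that year. It cannot occur with a January start. A year-only stop in the start year is imputed to 31 December and is not known to precede Revcovi, so treatment-emergent is defensible there.

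**Effect of the repair.** Running the same check against the imputed stop gave 0 misclassified cases in all 12 patterns. Of 158,656 test cases with partial dates and a true onset on or after Revcovi start, none was demoted. This follows by logic: the latest possible stop is never earlier than the true onset, so the reset date cannot fall before Revcovi start.

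**The case against.** The strongest case against is about size.

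- SAP 8.2 records only infections, clinically meaningful laboratory abnormalities and Revcovi-related events. In subjects new to Revcovi, related events cannot precede it, and laboratory findings normally carry a sample date. That leaves mainly prior infections whose end month is known and onset month is not.
- Protocol 12.3 asks for onset dates, and Protocol 14.7.1 provides manual queries for discrepant information.
- All analyses are descriptive, the error runs in the conservative direction for safety, and listings show the original partial dates, so an impossible record is visible.

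All of this stands and limits the weight of the point, but it does not make the rule correct. One could also read *complete* as complete after imputation, which would remove the problem. The SAP does not say so, and it places stop-date imputation after the check.

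Three stronger readings are tempting, and the documents do not support them.

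1. *Section 13.5 has the same fault.* It has no completeness condition. A reader might still note that in SAP 13.2 "the first dose of study medication is considered" Study Day 1, which for STP-2279-002 subjects is that study's first dose. The inference would be that an event with missing onset that resolved during that study becomes a registry treatment-emergent event. But the three periods in 13.5 and the algorithm in 14 use the registry start. SAP 5 and 7.2.3 keep data from that study out of the summary tables. Under SAP 8.2, events that began before the registry dose and continued past it "will be included in the AE listings but not in the summary tables". The wording is ambiguous; misclassification is not shown.
2. *Anti-infectives are affected too.* Their start dates are imputed "using the same algorithm described for adverse event onset dates". However, SAP 13.5 counts a drug only if it was applied on or after the registry start or continued until or after it. A drug with a latest stop of 31 March and a Revcovi start of 15 June meets neither condition.
3. *The grid share, or the share of months before the start month, is an error rate.* Both are conditional on the failing pattern and rest on assumed dates. Neither predicts how many records are affected.

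**Conclusion.** The point holds in a narrow form and is minor. Read plainly, SAP 14 classes an AE as treatment-emergent although its recorded stop month shows that it ended before Revcovi, when the onset month is unknown, the onset year is the year of Revcovi start, and the stop has month and year only. For Adagen-naïve and Adagen-transitioning subjects the same rule moves such an infection into Revcovi year 1.

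The error overstates treatment-emergent events. The number affected is unknown, because the documents give no count of partial dates, and it is probably small. The conclusion rests on taking *complete* to mean the stop date as recorded. If the author meant complete after imputation, the program may already be right and only the text needs correcting.

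**What to change.** In SAP 14, run the check after stop-date imputation. If the imputed onset falls after a complete stop date, or after the imputed (latest possible) date of a partial stop date, reset the onset to that date. Stops in the month of Revcovi start or later stay treatment-emergent, so the conservative intent is kept.

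In SAP 13.5, replace the reference to first dose of study medication with the registry's reported Revcovi start date, so that the exclusion uses the same anchor as the three period definitions above it. This is a harmonisation of wording.

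The cost is two sentences of SAP text and one condition in the date program. No new data are needed. A listing of records whose imputed onset falls after their imputed stop would show how many events are affected.
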